6.3.2.3. Other biopsy histological parameters

Definition

- SLIDE I
 - MFA (%) will be calculated as a mean of available fields at each evaluation
 - Adipose tissue (%) will be calculated as a mean of available fields at each evaluation
 - Other histological structure (%) will be calculated as a mean of available fields at each evaluation
 - Fibers with nuclear centralizations will be calculated at baseline and at Visit 11 according to the following formula:

$$Fibres\ with\ centralizations\ \%_{j} = \frac{\sum_{i=1}^{4} \frac{Fibres\ with\ nuclear\ centralizations_{ji}*100}{Total\ fibers\ number_{ji}}}{4}$$

where j = patient 1, 2... and i= field 1, 2, 3 or 4.

- Total number of fibers counted in slide I will be calculated as sum of the number of fibers of available fields at each evaluation
- SLIDE II

Sponsor: ITALFARMACO
Protocol: DSC/15/2357/53

 Regenerative fibers (MYH3) will be calculated at baseline and at Visit 11 according to the following formula:

$$Regenerative \ fibers \ \%_{j} = \frac{\sum_{i=1}^{4} \frac{(Regenerative \ fibers \ (MYH3)_{ji}) * 100}{Total \ fibers \ number_{ji}}}{4}$$
 where j = patient 1, 2... and i= field 1, 2, 3 or 4.

- Total number of fibers counted in slide II will be calculated as sum of the number of fibers of available fields at each evaluation
- SLIDE III
 - Cross Sectional Area (CSA) type I will be calculated at baseline and Visit
 11 according to the following formula:

$$CSA_{j} = \frac{\sum_{i=1}^{4} field_{ji}^{CSAI}}{\sum_{i=1}^{4} number \ of \ fields_{ji}^{CSAI}}$$

where j = patients 1, 2... and i = field 1, 2, 3 or 4.

 Cross Sectional Area (CSA) type II will be calculated at baseline and Visit 11 according to the following formula:

$$CSA_{j} = rac{\sum_{i=1}^{4} field_{ji}^{CSAII}}{\sum_{i=1}^{4} number\ of\ fields\ _{ji}^{CSAII}}$$

where j = patient 1, 2... and i= field 1, 2, 3 or 4.

Total Cross Sectional Area (CSA) will be calculated at baseline and Visit
 11 according to the following formula:

$$CSA_{j} = \frac{\sum_{i=1}^{4} field_{ji}^{CSAI} + field_{ji}^{CSAII}}{\sum_{i=1}^{4} number\ of\ fields\ _{ji}^{CSAII} + number\ of\ fields\ _{ji}^{CSAII}}$$

where j = patient 1, 2... and i= field 1, 2, 3 or 4.

- Total number of fibers counted in slide III will be calculated as sum of the number of fibers of available fields at each evaluation
- Fiber size variability will be calculated at baseline and Visit 11 as the median of the interquartile range (IQR) of total CSA according to the following formula:

Fiber size variability_i =
$$Q_{3i} - Q_{1i}$$

Ver.04 25Jun2020

Sponsor: ITALFARMACO
Protocol: DSC/15/2357/53

where j = patient 1, 2... and Q_1 and Q_3 are the first and third quartile for each patient (calculated among the 4 fields).

- Dystrophin
 - Total WB Dystrophin 1
 - Total WB Dystrophin 2

Analysis methodology

The absolute value of percentage of MFA and change versus baseline, at each time point, will be summarized as a continuous variable using descriptive statistics.

The absolute change in percentage of MFA after 12 months of therapy will be calculated as the difference between percentage of MFA at Visit 11 and its baseline value. This variable will be analyzed using an ANCOVA model with baseline percentage of MFA as covariate and treatment and concomitant steroid use at baseline as independent class variables. Results will be reported as Least-Square Means as well as difference between treatments together with their corresponding two-sided 95% CI. Possible need for log transformation of this variable will be assessed by check of ANCOVA model residuals. If considered non-Normal, a supportive analysis will be performed on the log scale.

The same analyses will be done for the adipose tissue (%), other histological structure, fibers with nuclear centralizations, regenerative fibers, CSA I, CSA II, Total CSA, Fiber size variability and percentage of dystrophin.

Total number of fibers counted in Slide I, II and III will be summarized as a continuous variable at each time point as well as change vs baseline using descriptive statistics.

A Mixed Model will be fitted to the data with the difference between visit 11 and baseline values as the dependent variable; baseline as a covariate, treatment will be included as independent class variables and treatment by sequence interaction. The sequence of biopsy site (Right-Left, Left-Right) will be included as a fixed effect and subject as a random effect to evaluate the difference in Total CSA between biopsy sites. The same evaluation will be done also for MFA %.

If the treatment by sequence interaction is p>0.10, then the model without the interaction term will be presented.

Data handling rules Primary analysis will be based on observed data only.

Sensitivity analyses for the histological endpoints will be performed as follow:

1. Multiple imputation for missing data:

Sponsor: ITALFARMACO
Protocol: DSC/15/2357/53

- a. Missing baseline primary endpoint data will be imputed as the mean of all non-missing baseline primary endpoint values across the randomized treatment groups. Visit 11 missing data will be imputed under a Missing At Random (MAR) assumption using SAS procedure MI within each treatment group using distribution implied by the non-missing patient data for that treatment group. A total of 20 imputation runs will be performed. Post imputation, each imputed dataset will be analysed separately exactly as described for primary efficacy analysis. The SAS procedure MIANALYZE will then be used to combine the 20 datasets of estimates by Rubin's rules. The resulting multiply imputed means and difference in means will be presented, along with the associated SEs, 2-sided 95% CIs and 2-sided p-values.
- b. Missing baseline primary endpoint data will be imputed as the mean of all non-missing baseline primary endpoint values across the randomized treatment groups. Visit 11 missing data will be imputed under a Missing Not At Random (MNAR) assumption using SAS procedure MI for both randomized treatment groups using the distribution implied by the non-missing patient data within the placebo group. A total of 20 imputation runs will be performed. Post imputation, each imputed dataset will be analysed separately exactly as described for primary efficacy analysis. The SAS procedure MIANALYZE will then be used to combine the 20 sets of estimates by Rubin's rules. The resulting multiply imputed means and difference in means will be presented, along with the associated SEs, 2-sided 95% CIs and 2-sided p-values.

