6.3.1. Primary efficacy analysis

Definition of primary endpoint

The primary endpoint is the mean change in total fibrosis comparing the histology of muscle biopsies before and after 12 months of treatment with givinostat versus placebo. The primary efficacy assessment for this study is the Total Fibrosis assessed through histological examination of muscle biopsies. A muscle biopsy was collected at the beginning and at the end of treatment to calculate the mean change from baseline to 12 months.

For each patient, the percentage of total fibrosis will be calculated as a mean of available fields at each evaluation.

Analysis methodology

The primary hypothesis to be tested is that total fibrosis (%) will increase less in the givinostat group than in the placebo group.

Since the blinded data at the time of the sample size re-estimation indicated the primary efficacy variable to be non-Normally distributed, the change in mean fibrosis from baseline to endpoint after 12 months of therapy will be analyzed on the log scale. Therefore, mean fibrosis at baseline and Visit 11 will be log transformed prior to analysis. An analysis of covariance (ANCOVA) model will be fitted to the data with the difference between log visit 11 and log baseline values as the dependent variable; log baseline value will be included as covariate and treatment and concomitant steroid use at baseline as independent class variables. LSmean values for the log change from baseline to visit 11 will be extracted, together with the associated log scale SEs; the difference in LSmean values will also be extracted as the measure of treatment effect along with corresponding log scale SE and two-

Sponsor: ITALFARMACO
Protocol: DSC/15/2357/53

sided 95% Confidence Interval (CI). LSmean values, the difference in LSmean values and the associated CI will be back transformed to the ratio scale for the purpose of presentation.

Summary descriptive statistics (N, geometric mean, %CV, mean, median, SD, min and max) for total fibrosis value and change versus baseline, at each time point, will be provided.

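### Two secondary histology formulas in the SAP divide by a fixed 4, so a biopsy with fewer than four readable fields gets an understated or an undefined percentage

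*SAP*

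**What the plan says.** SAP 6.3.2.3 gives a formula for fibres with centralised nuclei on slide I ("Fibers with nuclear centralizations will be calculated at baseline and at Visit 11 according to the following formula") and one for regenerative fibres on slide II ("Regenerative fibers (MYH3) will be calculated at baseline and at Visit 11 according to the following formula"). In each, the affected fibres in a field are expressed as a percentage of all fibres in that field. The percentages are summed from i = 1 to 4, and the sum is divided by the number 4. The index is explained as "where j = patient 1, 2... and i= field 1, 2, 3 or 4".

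Other definitions let the divisor follow the data:

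- **Slide I area percentages.** "MFA (%) will be calculated as a mean of available fields at each evaluation". Adipose tissue and other structures follow the same rule.
- **Fibre totals.** "Total number of fibers counted in slide I will be calculated as sum of the number of fibers of available fields at each evaluation". Slides II and III have the same rule.
- **Fibre cross-sectional area on slide III.** The formulas divide by a number-of-fields term, not by a constant.
- **Primary endpoint, SAP 6.3.1.** "For each patient, the percentage of total fibrosis will be calculated as a mean of available fields at each evaluation".

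Both fibre percentages are then analysed by ANCOVA on the absolute change from baseline to Visit 11, with the baseline value as covariate. The data-handling rules in SAP 4.4.2 and 6.3.2.3 deal with missing observations. They give no rule for a missing field within a biopsy.

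**The concern.** The SAP provides for unavailable fields on slides I and II, because it totals the fibres on those slides over the fields that are available. The two percentages taken from the same slides have no such provision. A formula in a SAP is a programming instruction, so this is a rule that fails in a situation the plan itself allows for.

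What is at stake is the value of two secondary histology measures. Regenerative fibres are named among the secondary endpoints in Protocol 5.2.2 and 13.6.2. Fibres with centralised nuclei are added by the SAP. An error in a single biopsy goes straight into the change score and, if it occurs at baseline, into the covariate as well. The planned arms are 34 and 17 patients, so a few affected biopsies could be noticeable. Two programmers following the text could also report different values for the same slide.

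**Working it through.** The SAP gives no worked figure to reproduce, so the check evaluates the printed formula directly.

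**Inputs from the SAP (6.3.2.3).** Four planned fields; divisor 4; analysis of change from baseline to Visit 11.

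**Assumptions, because the documents give no figures.** The number of readable fields k, from 1 to 4, and the underlying percentages used as illustrations.

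**Step 1: one biopsy, unread fields skipped in the sum.** Let S be the sum of the k available field percentages. The printed formula gives S/4 and the available-field mean is S/k. The ratio is (S/4)/(S/k) = k/4.

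| Fields read (k) | Ratio k/4 | Printed result if every field read shows 20% |
|---|---|---|
| 4 | 100% | 20% |
| 3 | 75% | 15% |
| 2 | 50% | 10% |
| 1 | 25% | 5% |

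With unequal fields of 12%, 18% and 22%, S = 52. The printed formula gives 52/4 = 13.0% and the available-field mean is 52/3 = 17.3%. If S = 0, both give 0%, so a true 0% is unaffected.

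**Step 2: change between visits, same reading.** With underlying values B at baseline and V at Visit 11, and field counts k_B and k_V, the printed change is V × k_V/4 − B × k_B/4.

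| Underlying values | Fields (baseline, Visit 11) | Printed change (points) | Underlying change (points) |
|---|---|---|---|
| 8% to 8% | 4, 3 | 6 − 8 = −2 | 0 |
| 20% to 20% | 4, 3 | 15 − 20 = −5 | 0 |
| 20% to 20% | 4, 2 | 10 − 20 = −10 | 0 |
| 20% to 20% | 3, 4 | 20 − 15 = +5 | 0 |
| 20% to 16% | 4, 3 | 12 − 20 = −8 | −4 |
| 20% to 16% | 3, 4 | 16 − 15 = +1 | −4 |
| 20% to 16% | 3, 3 | 12 − 15 = −3 | −4 |

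Unequal counts can therefore produce a false fall or a false rise. Equal reduced counts do not create a change out of nothing, but they shrink a real one by k/4: the last row shows 3/4 of −4.

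**Step 3: the other reading.** If the unread field is a missing term that propagates, the sum over four fields is undefined and so is the biopsy value. A biopsy with three readable fields then drops out of the observed-data analysis, although MFA from slide I would still be computed from its available fields.

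**Step 4: the amended formula.** Dividing S by k returns the available-field mean at every k. In the 20% illustration it gives 20% for k = 4, 3, 2 and 1. With k = 4 it is identical to the printed formula.

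**The case against.** Four fields are plainly the planned number. The same SAP section describes the quartiles for fibre size variability as taken among the 4 fields. If every biopsy yields four readable fields, the formula is exact, and nothing in the documents says how often that fails. This stands: the practical effect may be nil, and the percentages in the tables are illustrations.

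A reader might infer that the formula always lowers the value. The documents do not support that. The low value requires that the missing field be skipped, or counted as zero, while the divisor stays at 4. Read strictly, the sum has no value, and the consequence is a lost biopsy.

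A reader might also infer a bias in the treatment comparison. The documents give no reason why field counts should differ by arm, and Protocol 8.4 keeps histology personnel apart from the safety results that could hint at allocation. The false change can also go either way. What has been shown is error within a patient.

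Finally, a competent programmer might divide by the available fields anyway. That would depart from the written formula, and the SAP should not rely on it. None of these points removes the inconsistency, since no rule in the SAP says what to do with three fields.

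**Conclusion.** The inconsistency is real. As printed, the two formulas give a wrong or undefined value for a biopsy with fewer than four readable fields, whereas the neighbouring measures on the same slides are defined to cope with that case.

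If unread fields are skipped, the value is 75%, 50% or 25% of the available-field mean for three, two or one fields, except where the true value is 0%. If missing terms propagate, the biopsy is lost. These ratios are exact. How often they apply is unknown, and with four fields throughout the error is zero.

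The effect to expect is added error and attenuation in two secondary histology measures, only one of which the protocol names. The documents do not support reading this as a threat to the main result: total fibrosis is averaged over available fields and is not touched. It is a limited correction, but worth making before unblinding.

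**What to change.** In both formulas, let the sum run over the available fields with a non-zero fibre count for that patient and evaluation, and divide by the number of those fields instead of 4. The condition on the fibre count is needed because a field without fibres has no percentage. This matches the rule the SAP already uses for MFA, adipose tissue and total fibrosis. It would also help to state the minimum number of fields for a biopsy to count as evaluable on these measures.

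The cost is an edit to two formulas and the matching program lines. Results do not change for any biopsy with four usable fields, and no new data are needed.

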	 3- Total Cross-Sectional Area (CSAI and CSAII) 4- Total number of fibers counted in slide III 5- Fiber size variability - Dystrophin 1- Total WB Dystrophin 1 and Total WB Dystrophin 2 	
To establish the efficacy of givinostat versus placebo administered chronically over 12 months in slowing disease progression.	Motor Function Measurement (MFM): 1- Standing and transfers (D1) 2- Axial and proximal motor function (D2) 3- Distal motor function (D3) 4- Total score (Total mark)	Mean change in MFM before and after 12 months of treatment with givinostat versus placebo.
	Time Function Tests (TFT): 1- 4-Stair ascent duration 2- Rising from floor duration 3- 10-Metre Walk/Run test duration	Mean change in Time Function Tests (time to climb four standard steps, time to rise from floor and time to walk/run 10 m) before and after 12 months of treatment with givinostat versus placebo.
	Functional Tests:	
	1- Distance walked after 6 minutes (6MWT)	Mean change in 6MWT distance before and after 12 months of treatment with givinostat versus placebo.
	2- Patients with < 10% worsening in 6MWT	Number and proportion of patients with < 10% worsening in 6MWT at the end of study will be compared between treatment groups.

OBJECTIVES	VARIABLES	ENDPOINTS
	3- Patients who lose ambulation during the study (6MWT not done because patient unable to physically perform the test)	Number and proportion of patients who lose ambulation during the study will be compared between treatment groups.
	4- Patients who lose the ability to rise from floor (Rise From Floor grading = 0)	Number and proportion of patients who lose the ability to rise from floor (from baseline through end of study) will be compared between treatment groups.
	Muscle strength measured by Hand Held Myometry (HHM):	Mean change in muscle strength (right/left knee
	 Left knee extension measurements Right knee extension measurements Left elbow flexion measurements Right elbow flexion measurements 	extension and right/left elbow flexion) before and after 12 months of treatment with givinostat versus placebo.

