3.5. Sample Size and Power Estimation

The hypothesis to be tested in this study is as follows:

$$H_0: \mu_G - \mu_P = 0$$
 vs $H_1: \mu_G - \mu_P \neq 0$

where μ_G and μ_P the mean change from baseline to 12 months in total fibrosis (%) for the givinostat and placebo groups respectively.

The primary hypothesis to be tested in this study is that total fibrosis (%) will increase less in the givinostat group than in the placebo group so the primary efficacy variable of the study is the mean change from baseline to 12 months in total fibrosis (%).

Ver.04 25Jun2020

Sponsor: ITALFARMACO Protocol: DSC/15/2357/53

A sample size of 48 patients with evaluable baseline biopsies (in a 2:1 ratio, 32 and 16 respectively) will provide 80% power to test the null hypothesis of no treatment effect (givinostat – placebo) on total fibrosis vs the alternative hypothesis that the treatment effect is \geq 9% using a two-sided t-test with alpha level of 5% and assuming a common SD of 10% (with the SD being based upon blinded interim data from first 20 patients with valid biopsies).

Allowing for an approximate 5% of patients with not evaluable biopsies, the total number of patients to be randomized is 51 (i.e. 34 in givinostat arm and 17 in placebo arm).

After the first 20 baseline muscle biopsies was collected, an interim blinded sample size reassessment was undertaken to check the SD assumption used in sizing the trial. Details are capture in the specific SAP for the Interim Analysis.

After study enrollment was completed and baseline data were collected for all patients, a second blinded interim analysis was performed to obtain a preliminary overview of the baseline patient characteristics.

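### The Total CSA formula in SAP 6.3.2.3 divides by the type II field count twice, so it is wrong whenever type I and type II field counts differ within a biopsy

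*SAP*

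**What the plan says.** SAP section 2 lists the variable as "Total Cross-Sectional Area (CSAI and CSAII", that is, both fibre types together. SAP 6.3.2.3 then gives three related formulas for slide III, each summing over fields 1 to 4:

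- CSA type I: type I field values divided by their own count, "number \ of \ fields_{ji}^{CSAI". CSA type II has the same form with type II terms.
- Total CSA, numerator: "field_{ji}^{CSAI} + field_{ji}^{CSAII".
- Total CSA, denominator: "number\ of\ fields\ _{ji}^{CSAII} + number\ of\ fields\ _{ji}^{CSAII".

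Total CSA is an analysed variable. The change from baseline is tested with the histology ANCOVA, whose list of variables includes "CSA I, CSA II, Total CSA, Fiber size variability and percentage of dystrophin". It is also the outcome of a mixed model with biopsy sequence, fitted "to evaluate the difference in Total CSA between biopsy sites". The multiple-imputation sensitivity analyses for histological endpoints are in the same section.

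**The concern.** The denominator disagrees with its own numerator, with the two single-type formulas beside it, and with the definition in section 2. A mean over all available type I and type II field values must be divided by the number of such values. As printed, it is divided by twice the type II count.

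The CSA formulas use field counts for each type instead of a fixed 4, unlike the formulas for centralised nuclei and regenerative fibres in the same section. If one fibre type has fewer usable fields than the other, those counts should make the mean correct, and the printed version fails there. A programmer who follows the SAP would code the error; one who silently corrects it would depart from the SAP. At stake is the level of a secondary histology variable and, under a further condition shown below, its change from baseline.

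**Working it through.** The documents report no figure computed from this formula, so there is nothing to reproduce. The check is algebra followed by an illustration.

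**Inputs.** nI and nII are the readable type I and type II fields in one biopsy, each at most 4 (SAP 6.3.2.3). aI and aII are the mean field values for each type. For scale, the blinded interim CSA mean is 4871.68 µm² and the SD 1904.86 µm² (Protocol 13.10, SAP 6.6). Setting aI = aII = 4871.68 is an assumption made for illustration; the ratio below does not depend on it.

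**Formulas.**

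- Printed: (nI·aI + nII·aII) / (2·nII)
- Intended: (nI·aI + nII·aII) / (nI + nII)
- Ratio, printed to intended: (nI + nII) / (2·nII)

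**Level of Total CSA in one biopsy (intended value 4871.68 in every row).**

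| nI / nII | Ratio | Printed value (µm²) | Error (µm²) |
|---|---|---|---|
| 4 / 4 | 8/8 = 1 | 4871.7 | 0 |
| 3 / 3 | 6/6 = 1 | 4871.7 | 0 |
| 4 / 3 | 7/6 = 1.167 | 5683.6 | +811.9 |
| 3 / 4 | 7/8 = 0.875 | 4262.7 | −609.0 |
| 4 / 2 | 6/4 = 1.5 | 7307.5 | +2435.8 |
| 2 / 4 | 6/8 = 0.75 | 3653.8 | −1217.9 |

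Over all counts from 1 to 4 the ratio runs from 5/8 = 0.625 (1 / 4) to 5/2 = 2.5 (4 / 1). With nII = 0 the printed formula is undefined even though type I data exist. The +811.9 for 4 / 3 is 811.9/1904.86 = 0.43 of the interim SD.

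**Change from baseline, no true change.**

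- 4/4 at baseline, 4/3 at Visit 11: 5683.6 − 4871.7 = +811.9, a false change.
- 4/4 at baseline, 3/4 at Visit 11: 4262.7 − 4871.7 = −609.0, a false change.
- 4/3 at both visits: 0.
- 3/3 at baseline, 4/4 at Visit 11: 0.

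**Change from baseline, true change +500, counts 4/3 at both visits.** The printed formula gives 500 × 7/6 = +583.3. The same imbalance at both visits rescales a true change but does not create one.

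**The case against.** The strongest reply is that this may not be an error in the SAP at all. The equation was read from PDF by a program, and the fault is one superscript, I versus II. Nearby text shows similar slips: the variable list in SAP section 2 gives type II area the type I abbreviation, and the fibre size variability formula indexes the patient inconsistently. Intent is clear from the numerator, the sibling formulas and the definition. This stands as a reason to check the source first, and it limits the fault to a typographical one. It does not make the text usable as it reads.

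The second reply is that the trigger is not shown to occur. Both types are read on slide III, so losing a field would ordinarily remove both, and equal counts give the right answer. The SAP's allowance for missing fields, for example "number of fibers of available fields at each evaluation", is fully explained by loss of whole fields. This also stands: no passage says a field can be usable for one type and not the other, and none rules it out.

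Three stronger readings are tempting, and the documents do not support them:

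- A reader might infer that any missing field produces a spurious change. It does not. The type I and type II counts must differ within a biopsy, and their ratio must differ between visits.
- A reader might set the 812 µm² beside the mean CSA change of 865.27 µm² in the DMD study (Protocol 4.2.2). That compares one hypothetical patient's error with a group mean change from baseline in an open-label study. One such patient would move an arm mean by 811.9/34 = 23.9 µm² (givinostat) or 811.9/17 = 47.8 µm² (placebo), taking the planned arm sizes, and nothing suggests the error would favour one arm.
- A reader might argue that even the corrected formula should weight by fibre number. Averaging over fields is the SAP's stated convention for total fibrosis and the other histology percentages. The documents describe only a total slide III fibre count, not counts by type. Weighting is a different choice of definition, not a correction.

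**Conclusion.** Wrong as written; minor severity. Read literally, the formula misstates Total CSA by the factor (nI + nII)/(2 nII) whenever the two counts differ within a biopsy, and is exact otherwise. The size in the trial cannot be stated, because the documents do not give the frequency of unequal counts; it may be nil.

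The conclusion rests on two assumptions: that the extracted equation matches the source SAP, and that the program follows the SAP literally. If either fails, there is no numerical consequence. CSA was the primary endpoint before Amendment 4, but that does not raise the severity now: Total CSA is one of several secondary histology variables. Total fibrosis has its own definition in SAP 6.3.1, and the sample size is built on total fibrosis, "assuming a common SD of 10" percent, so neither is touched.

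**What to change.** 1. Compare the Total CSA denominator in the source SAP, and in the analysis program, with the text quoted above.
2. If the type II count is repeated in either, replace one term so that the denominator is the number of type I fields plus the number of type II fields. Put brackets around the two summed terms in numerator and denominator so that the summation clearly covers both.
3. Optionally, report how many biopsies have unequal type I and type II field counts at each visit, which would settle whether the point ever mattered.

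The cost is one term in one SAP formula and, if it was coded as printed, one line of program. No new data are needed and no other analysis changes.

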### Interim analysis:

No formal interim efficacy analysis is planned. After the first 20 baseline biopsies were collected, a descriptive blinded interim analysis was performed aimed at checking the real variability of the primary endpoint under observation in the previous protocol study.

The histopathological features observed in this blinded interim analysis showed that the mean CSA of the biceps fibers in BMD (mean: 4871.68 µm²; min 1933.49 µm²; and max 9446.34 µm²; and S.D.: 1904.86 µm²) is similar to the age-matched CSA in male adult healthy individuals, although with a larger degree of fiber size variability due to a substantial number of both hypertrophic and hypotrophic fibers. As a consequence, the likelihood that givinostat can increase the CSA of fibers further is low and also it is doubtful that a further increase in fiber CSA would be beneficial. The histopathological features observed in these preliminary biopsies showed also significant fibro-adipose replacement, which can be considered the hallmark of the disease. The change of total fibrosis is considered a more indicative outcome measure of the possible effect of givinostat relative to the assessment of CSA and, hence, it is to be evaluated as the primary endpoint for the trial.

After study enrollment is completed and baseline data are collected for all subjects, a second blinded interim analysis will be performed to obtain a preliminary overview of the baseline patient characteristics.

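### SAP 6.3.2.3 defines fiber size variability as a median of IQRs in words but as one Q3 − Q1 among the fields in its formula, which read literally can miss the spread of individual fibres

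*SAP*

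**What the plan says.** In SAP 6.3.2.3, under Slide III, the sentence reads: "Fiber size variability will be calculated at baseline and Visit 11 as the median of the interquartile range (IQR) of total CSA". The formula that follows is a single difference, Q3 − Q1, and its legend says that "Q_1 and Q_3 are the first and third quartile for each patient (calculated among the 4 fields".

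The CSA formulas just above it, for type I, type II and total, sum field values and divide by a count of fields. Their legend is "where j = patients 1, 2... and i = field 1, 2, 3 or 4" (type I formula; the others match). There is no index for a single fibre. Fibre counts appear only as a separate descriptive item: "Total number of fibers counted in slide III will be calculated as sum of the number of fibers of available fields at each evaluation".

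The variable is analysed like MFA (%), by ANCOVA with LS means, a treatment difference and a 95% CI. The list of parameters so treated includes "Total CSA, Fiber size variability and percentage of dystrophin".

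The Protocol Synopsis (Interim analysis) uses the term for the mix of large and small fibres. Mean CSA resembles that of healthy adults, "although with a larger degree of fiber size variability due to a substantial number of both hypertrophic and hypotrophic fibers". SAP 6.6 says the same.

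**The concern.** A median of IQRs needs several IQRs per patient, and the formula yields one. Two programmers working from this section could produce different variables.

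The second problem is what the formula measures. If each field contributes a field-level CSA, quartiles among the fields describe how much fields differ from one another. A biopsy with many hypertrophic and hypotrophic fibres, mixed evenly across its fields, would score low. The treatment comparison would then say little about the feature the variable is named for. If the definition is settled only after unblinding, it becomes a post-hoc choice.

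**Working it through.** The documents give no figure for this variable, so there is nothing to reproduce. The check compares three readings:

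- **A, literal formula:** Q3 − Q1 of the four field mean areas.
- **B, the sentence:** Q3 − Q1 over fibres within each field, then the median over fields.
- **C, pooled:** Q3 − Q1 over all fibres in the four fields together.

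**Worked example.** Four identical fields, each with fibres of 1000, 3000, 5000, 7000 and 9000 µm².

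- A: every field mean is 5000, so Q3 − Q1 = 0.
- B: each field has Q3 − Q1 = 7000 − 3000 = 4000, and the median is 4000.
- C: 4000.

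**Simulation inputs.** From the Protocol Synopsis: "mean CSA of the biceps fibers in BMD (mean: 4871.68" µm²). Assumed, not in the documents: lognormal fibre areas with within-patient CV 0.3 to 0.7, 50 to 200 fibres per field, true field-to-field CV 0 or 0.10. There were 3000 simulated patients per scenario, with quartiles from the empirical distribution with averaging.

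| Fibre CV | Fibres/field | Field CV | A | B | A/B |
|---|---|---|---|---|---|
| 0.3 | 200 | 0 | 137 | 1856 | 7% |
| 0.3 | 50 | 0.10 | 703 | 1833 | 38% |
| 0.5 | 50 | 0 | 460 | 2804 | 16% |
| 0.5 | 200 | 0 | 229 | 2814 | 8% |
| 0.3 | 200 | 0.10 | 654 | 1855 | 35% |
| 0.7 | 200 | 0.10 | 722 | 3500 | 21% |

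The first two rows are the extremes over all scenarios. A repeat run put the upper end at 39%. C stayed close to B throughout (1853 to 3530).

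**Hand check of the extremes.** With averaged quartiles, A for four values is half the outer range plus half the inner range. The expected order statistics of four standard normal values are ±1.029 and ±0.297, so A is about (1.029 + 0.297) = 1.326 SDs of a field mean.

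- Lower: SD = 4871.68 × 0.3/√200 = 103.3, and 1.326 × 103.3 = 137.
- Upper: SD = 4871.68 × √(0.09 × 1.01/50 + 0.01) = 529.6, and 1.326 × 529.6 = 702.

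**Quartile convention.** With linear interpolation, A becomes 0.5 × 1.029 + 1.5 × 0.297 = 0.960 SDs, a factor of 0.960/1.326 = 0.72. B hardly moves. The range of 7–38% falls to about 5–28%.

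**What A responds to.**

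- With field CV 0.10 and 200 fibres, raising fibre CV from 0.3 to 0.7 moves A by 722/654 = 1.10, while B moves by 3500/1855 = 1.89.
- With no true field differences, A does rise with fibre spread, but only through sampling error. It halves (460 to 229) when fibres per field go from 50 to 200 at the same fibre CV.
- The patient-to-patient sampling CV is 0.43–0.46 for A, against 0.05–0.12 for B.

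**The case against.** The SAP never says that a field value is an average of fibres. The phrase about the 4 fields could mean fibres pooled over the fields, or an IQR per field followed by a median. Either would measure fibre spread. Total CSA is built from a type I and a type II value per field, so the quartiles might run over eight values. The median might describe a summary across patients. The variable is also minor: Protocol 5.2.2 and 13.6.2 name CSA, MFAF and regenerative fibers among the other histology parameters, not this one.

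Much of this stands as evidence that the intent is uncertain. None of these readings is written in the SAP, and they do not all remove the problem:

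- Pooling leaves the median in the sentence unexplained.
- Eight type-by-field values would add the difference between fibre types, but still not the spread among individual fibres.
- A median across patients cannot define a per-patient value entered in an ANCOVA.

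A reader might infer more than the documents support:

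- **That the variable is certainly pure sampling noise between fields.** True field differences would also enter it, and the content of a field value is an inference from the field-count denominators and the single-fibre scale of CSA.
- **That the reported SD of 1904.86 µm² gives the fibre spread.** It comes from the first 20 baseline biopsies, and Protocol 13.10 compares it with the SD used for the original sample size. It therefore appears to be a between-patient SD.
- **That fibre-size heterogeneity is the sponsor's hallmark of the disease.** The Synopsis and SAP 6.6 give that role to fibro-adipose replacement.

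**Conclusion.** The point holds as a defect in one derivation rule. The sentence and the formula disagree on the page; that needs no assumption. Read literally with the field-level values the section defines, the formula mainly reflects differences between fields and can be near zero in a patient with very heterogeneous fibres.

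The size, roughly 7–39% of the within-field IQR with averaged quartiles and lower with interpolation, rests on the assumed fibre CV, fibre counts and field CV, and on field values being fibre means. It should be read as a range under those assumptions, not as an estimate for this trial.

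The consequence is small. It concerns one secondary histology parameter, tested without alpha adjustment. Nothing here touches total fibrosis or the sample size.

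**What to change.** Before unblinding, amend SAP 6.3.2.3 so that the formula and the sentence agree:

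- Compute Q3 − Q1 over individual fibre areas, type I and type II together, within each field.
- Take the median of those IQRs over the available fields at baseline and at Visit 11, which also settles the case of fewer than four fields.
- Name the quartile definition.

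If individual fibre areas were retained, this costs one definition and its program and uses measurements already made. The documents do not say whether they were retained, so the sponsor should confirm this first. If they were not, the variable should be relabelled as between-field variability of CSA and not interpreted as fibre-size spread.
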